1.3. In-hospital cardiac arrest

Until recently, no validated risk models existed for predicting outcomes following in-hospital cardiac arrest. The National Cardiac Arrest Audit (NCAA), the national clinical audit of in-hospital cardiac arrest coordinated by ICNARC in collaboration with the Resuscitation Council (UK), was therefore established with a dataset including established important risk factors for outcomes following in-hospital cardiac arrest with a view to subsequent development of a risk model. In the previous research study, we developed and validated two novel risk models for in-hospital cardiac arrest. Based on over 14,000 in-hospital cardiac arrests in 122 hospitals, risk models were developed to predict both return of spontaneous circulation (ROSC) greater than 20 minutes and survival to hospital discharge. These models demonstrate good discrimination (c index 0.72 and 0.81, respectively) in external validation data and have enabled risk-adjusted comparisons among hospitals to be included, for the first time, in routine reporting for NCAA.

Simultaneous to our work developing risk models for NCAA, a risk model for predicting hospital mortality following in-hospital cardiac arrest was published from the United States Get With the Guidelines—Resuscitation registry. This identified largely similar risk factors to the NCAA risk models, but included additional predictors not available in the NCAA dataset, most notably preexisting comorbidities. Data linkage with HES will enable calculation of comorbidity indices from diagnoses and procedural codes recorded during the hospital episode, an approach that has recently been applied successfully in the UK Renal Registry. Combining this information with the existing risk factors will enable us to determine the contribution of chronic health conditions to outcome from in-hospital cardiac arrest with a view to either routinely linking data in the future, or establishing which comorbidity fields are important to collect directly within NCAA.

While many patients do not survive the initial resuscitation attempt, the treatment of those that do requires substantial resources and many patients will be admitted to a critical care unit. Data linkage between NCAA and the CMP will allow us to better understand patterns of critical care resource use and organ support following successful resuscitation and develop prediction models for likely resource use.

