3.2. Sampling

The selection of sites is based on those participating in the CMP and NCAA.

The coverage of the CMP is extremely high, with 256 critical care units participating including over 97% of NHS adult general critical care units in England and Wales. We will link data for the period

1 April 2009 to 31 March 2015, enabling exploration of trends and fit of models over time, although only data from the last two years will be used to fit the final models as our previous research has established that the fit of risk models deteriorates over time. This will give a total sample size of over 850,000 admissions (700,000 critical care unit survivors) for exploring trends and fit over time with 330,000 admissions (280,000 critical care unit survivors) for model fitting. As the CMP is an ongoing programme, additional data will accrue while the development work is ongoing. At one year into the study, an additional 170,000 admissions (150,000 critical care unit survivors) will be available and the linkage will be updated providing data for external validation.

Of twenty-seven specialist cardiothoracic critical care units providing Level 3 (intensive) care, eight currently participate in the CMP. From 1 April 2009 to 31 March 2015 we will have a sample size of approximately 34,000 admissions to these units (3,000 deaths) for objective 2. The updated data linkage will include an additional 2,300 admissions (200 deaths) for external validation.

The coverage of NCAA is increasing and now stands at 181 hospitals, including over 75% of acute hospitals in England and Wales. From 1 April 2011 to 31 March 2015 we will have a sample size of approximately 56,000 in-hospital cardiac arrests (10,000 survivors) for objective 3. The updated data linkage will include an additional 16,000 in-hospital cardiac arrests (3,000 survivors) for external validation.

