5.1.2. Internal and external validation

Each newly developed or revised risk prediction model will be validated using the above measures both within the development sample and in independent validation data.

Where a prognostic model is based on a very large sample size and relevant variables are included in the final model, optimism is small and so, the apparent estimates of model performance (*c* index and Brier's score in the development data) are attractive because of their stability^[25]. However, to assess optimistic performance within the development data, the percentage of over-fitting will be estimated by the optimism-corrected statistics.

Where existing risk prediction models are modified, the performance of the revised model will be compared with the existing model using reclassification techniques. The improvement in reclassification will be quantified as the Net Reclassification Improvement NRI. We will calculate the NRI both using pre-defined categories of risk and also as a continuous measure (i.e. the proportion with any improvement in predicted risk compared against the proportion with any worsening in predicted risk).

After one year, the data linkage will be updated to provide an additional year of data to serve as independent validation data.

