5.2.2. Risk models for cardiothoracic critical care (objective 2)

5.2.2.1. Mortality at discharge from acute hospital (objective 2a)

Outcome defined as mortality at discharge from acute hospital (acute hospital mortality), as used for the current risk model.

Patients included in the model will be all those admitted to a participating cardiothoracic critical care unit.

New risk factors, pre- and intra-operative risk factors obtained by data linkage with the National Adult Cardiac Surgery Audit (see Apendeix 1), will be assessed for their optimal functional form (see Appendix 2).

The starting point for the new risk model will be the previously developed risk model using CMP data only.

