5.2.3. Risk models for in-hospital cardiac arrest (objective 3)

5.2.3.1. ROSC greater than 20 minutes and survival to hospital discharge (objective 3a)

Outcomes defined as ROSC greater than 20 minutes and survival to hospital discharge (hospital survival) from the existing NCAA data, the outcomes for the current risk models.

Patients included in the models will be all patients (aged 28 days or over) who received chest compressions and/or defibrillation following an in-hospital cardiac arrest and were attended by the hospital-based resuscitation team.

The starting point for the new risk models will be the previously developed risk models for each outcome.

New risk factors: pre-arrest risk factors obtained by data linkage with HES, the Charlson comorbidity index ^[28] and Elixhauser comorbidity measure ^[29] will be derived from International Classification of Disease (ICD-10) diagnostic codes and Office of Population Censuses and Surveys (OCPS) procedural codes, using methods employed recently by the UK Renal Registry ^[16], will be assessed for the optimal categorisation of the complex categorical risk factors.

5.2.3.2. Survival to 30 days, 90 days and 1 year and time to death (objective 3b)

Outcome defined as mortality at 30-days, 90-days and 1-year and days from cardiac arrest to death using the date of death obtained by data linkage with ONS.

Patients included in the models will be all patients (aged 28 days or over) who received chest compressions and/or defibrillation following an in-hospital cardiac arrest and were attended by the hospital-based resuscitation team.

The starting point for each new risk model will be the risk model for survival to hospital discharge developed in objective 3a.

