Appendix 2 Approach to model development

For each newly developed or revised risk prediction model, we fill adopt the following general approach to model development.

- 1. Potential predictors will be identified and patterns of missing data within the potential predictors will be explored, with particular attention to the completeness and accuracy of data linkage between the databases. Approaches to handling the missing data will be compared, based on the best performing approaches from previous work.
- The most appropriate functional form for each potential predictor will be explored, taking
 into consideration the use of continuous non-linear models (e.g. restricted cubic splines or
 right-restricted cubic splines) for continuous predictors and appropriate categorisation and
 structure of categorical predictors.
- 3. A main effects model will be fitted through a process of deleting terms, re-fitting and verifying, using: likelihood ratio tests to remove non-significant predictors; and the Bayesian Information Criterion (BIC)^[30] as the basis to determine which predictors make an important contribution to the fit of the model.
- 4. The functional form of each predictor included in the main effects model will then be reexamined to confirm if any changes are required based on adjustment for other important predictors.
- 5. Finally, interactions between the predictors will be introduced based on clinical input to identify and prioritise the potentially important interactions to consider and avoid over fitting, with interactions retained if they have a positive effect on the BIC.

For objectives 2a and 3a: the addition of new predictors to existing models will be considered and then the effect of those predictors previously included in the risk model will be re-assessed to determine whether they still make an important contribution to the model (see above).

For objectives 2b and 3b: the risk model will be re-fitted to the new outcome, predictors that were previously considered but were found not to be important predictors for hospital survival will be reassessed by adding them to the model and finally the effect of those predictors previously included in the risk model will be re-assessed to determine whether they still make an important contribution to the model (see above).

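### The reclassification comparison in section 5.1.2 makes no provision for refitting the existing model, so its NRI can mix coefficient updating with the value of the linked predictors

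*Protocol*

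**What the plan says.** Protocol section 5.1.2 fixes the comparison and the measure: "Where existing risk prediction models are modified, the performance of the revised model will be compared with the existing model using reclassification techniques", and "We will calculate the NRI both using pre-defined categories of risk and also as a continuous measure". It explains the continuous version as "the proportion with any improvement in predicted risk compared against the proportion with any worsening in predicted risk", without mentioning events and non-events separately.

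The comparators can be identified. For objective 2a (section 5.2.2.1): "The starting point for the new risk model will be the previously developed risk model using CMP data only". For objective 3a (section 5.2.3.1): "The starting point for the new risk models will be the previously developed risk models for each outcome". Appendix 2 describes how the revised models are built: "the addition of new predictors to existing models will be considered", after which the old predictors are assessed again. The revised models are therefore fitted to the new linked data.

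Section 3.2 limits final model fitting in general critical care to the last two years because "our previous research has established that the fit of risk models deteriorates over time". Section 1.3 says what the comorbidity linkage for cardiac arrest is meant to inform: "with a view to either routinely linking data in the future, or establishing which comorbidity fields are important to collect directly within NCAA".

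**The concern.** Read naturally, the comparison sets an older equation, with coefficients from an earlier period, against a new equation with extra predictors and coefficients fitted to recent data. NRI responds to any change in predicted risk, and so to recalibration as well as to added information. If the older equation no longer fits, part or all of the NRI may reflect updating.

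This matters because objectives 2a and 3a exist to find out what cardiac surgery audit fields and hospital comorbidity codes add. For cardiac arrest, the answer feeds a choice between routine linkage and new audit fields. A misleading NRI could favour data collection that adds nothing, or hide a useful predictor.

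**Working it through.** **Is there a figure to reproduce?** No. The protocol sets no NRI target for this comparison. The 23% NRI in section 1.1 belongs to the general critical care model and cannot be rebuilt from what is given.

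**Inputs from the protocol**
- Objective 2a: existing c index 0.90 (section 1.2); event rate 3,000/34,000 = 8.8% (section 3.2).
- Objective 3a, hospital survival: existing c index 0.81 (section 1.3); event rate 10,000/56,000 = 17.9% (section 3.2).

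The 3,000 deaths equal 34,000 admissions minus the 31,000 unit survivors in the synopsis. They may therefore be unit deaths, in which case 8.8% only approximates hospital mortality.

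**Assumptions, not in the protocol**
- Linked predictors have exactly zero effect.
- The old model has an observed/expected ratio (O/E) of 0.8 to 1.2 and a calibration slope *b* of 0.8 to 1.2.
- Category cut-points are 5/10/20% for 2a and 5/10/20/40% for 3a.

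**Set-up.** Let *L* be the correct current log odds, which the revised model recovers. Take *L* as normal, with mean and SD chosen to give the event rate and c index above (for 3a, mean −2.04 and SD 1.40). The old model predicts

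L_old = k + L/b,

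with *k* set to give the assumed O/E. Then

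continuous NRI = [P(up | event) − P(down | event)] + [P(down | non-event) − P(up | non-event)].

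**What slope drift does.** For b > 1 a patient moves up when L > k + L/b, that is, when L exceeds t = k/(1 − 1/b). Hence

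NRI = 2 × [P(L > t | event) − P(L > t | non-event)].

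This is twice the sensitivity plus specificity minus one of the *old* score at cut-point t. It reflects discrimination that the old model already had. For b < 1 the direction reverses and the sign is negative.

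- 2a, b = 1.1, O/E 1: event part +0.361, non-event part +0.810, sum +1.171. With b = 1.2 the sum is +1.179, so doubling the drift hardly changes it.
- 3a, b = 1.1, O/E 1: +0.286 + 0.614 = +0.900.
- 3a, b = 0.9, O/E 1: −0.259 − 0.633 = −0.892.

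**Results with linked predictors worth nothing**

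| Assumed state of the old model | Continuous, 2a | Continuous, 3a | Categorical, 2a | Categorical, 3a |
|---|---|---|---|---|
| Slope 1.1, mean risk correct | +1.17 | +0.90 | +0.013 | +0.068 |
| Slope 0.9, mean risk correct | −1.15 | −0.89 | −0.010 | −0.066 |
| Intercept only, O/E 0.8 to 1.2 | 0 | 0 | −0.007 to +0.037 | −0.009 to +0.066 |
| Relative weights misplaced by 0.1 to 0.3 | +0.06 to +0.19 | +0.04 to +0.13 | +0.01 to +0.08 | +0.01 to +0.07 |
| Whole O/E and slope grid | −1.27 to +1.27 | −0.90 to +0.90 | −0.04 to +0.06 | −0.13 to +0.21 |
| Old predictors refitted on the same data | 0 | 0 | 0 | 0 |

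In the two slope rows the c index does not change, because the ranking is the same, and the Brier score changes by less than 0.0003.

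**Cut-points.** With cut-points of 5/10/20/40/60%, correcting a 10% slope drift gave a categorical NRI of +0.05 to +0.11. That range also covers the model for return of spontaneous circulation (c index 0.72), at an assumed 45% event rate.

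**The definition read literally.** If all patients are pooled, intercept drift no longer cancels. At O/E 0.9 every prediction falls, so every non-event improves and every event worsens: 0.912 − 0.088 = +0.82 for 2a and 0.821 − 0.179 = +0.64 for 3a. At O/E 1.1 the signs reverse.

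**The case against.** Several points on the other side are sound.

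- **The text does not say that the comparator is left unrefitted.** A reader might infer that it does; in fact it neither requires nor rules out refitting, and an analysis plan that is not shown may settle this. But section 5.1.2 already names the comparator and the measure, and followed as written it leads to the mixed comparison.
- **NRI is not said to measure the linked predictors alone.** Appendix 2 retains predictors by likelihood ratio tests and BIC within the newly fitted model, which drift in the old coefficients does not distort. No passage ties the linkage decision to NRI. This stands and limits the consequence. Still, NRI is the stated measure of improvement over the existing model.
- **The c index, Brier score and calibration are also planned.** They would help to expose a pure slope artefact. They are required for each new or revised model, but not explicitly for the old model beside it.
- **Comparison with the model in use is legitimate.** Objective 4a is adoption into routine audit reporting, so this result is worth keeping, under its own label.
- **Drift is not reported for these models.** The sentence in section 3.2 speaks of fit, gives no size or direction, and sits in the general critical care paragraph. The cardiothoracic and arrest models come from the immediately preceding study, so drift may be small. Against that, the arrest models used over 14,000 arrests in 122 hospitals, while the audit now covers 181 hospitals and about 56,000 arrests, so some misfit is plausible.

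A reader might also infer that drift will be credited to the new predictors, always upwards. The calculation contradicts this: the effect can be positive, zero or negative. Nor should these values be set against the 23% in section 1.1, whose NRI type and cut-points are not given.

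**Conclusion.** The concern holds in limited form. For objectives 2a and 3a, section 5.1.2 read naturally gives an NRI that combines updated coefficients with linked predictors, and the two cannot be separated afterwards. Under an assumed 10% slope drift with mean risk correct, the artefact in the continuous NRI is about ±0.9 (3a, hospital survival) or ±1.15 (2a), with almost no change in Brier score. It is zero for intercept-only drift on the usual event-plus-non-event sum, and small and positive when only relative weights have shifted. Categorical values depend on cut-points that the protocol does not give.

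These figures show how sensitive the measure is; they do not forecast the bias in this study. They rest on a normal distribution of log odds, the protocol's c indices and event rates, and a drift whose size and direction are unknown. Which predictors enter the models is not in question. What is affected is how the improvement is quantified and explained.

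**What to change.** In section 5.1.2, state that:

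1. The increment from linked predictors is judged against the existing predictor set refitted on the same development data and the same linked patients as the revised model. Recalibrating intercept and slope removes intercept and slope drift; shifts in individual coefficients need the full refit.
2. The changes in c index and Brier score in the validation data are reported next to the NRI, with its event and non-event parts shown separately.
3. The comparison with the as-published model is kept as a separate result, labelled as the total gain including updating.

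The same-patients condition matters because, under section 4.1, the external audits return only successfully linked records.

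The cost is one extra model fit per comparison and a few lines of text. The improvement attributed to linkage may look smaller than against the as-published model.

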5.1.3. Approach to model development

The model building process will consist of a number of stages described in Appendix 2.

5.1.4. Analysis of outcome measures

The analysis plans will be finalised with input from the Clinical Advisory Groups prior to modelling.

The following approaches for model development will be applied depending on the outcome and objectives of the analysis:

- To model mortality at fixed time-points (hospital discharge, 30 days, 90 days, 1 year), ROSC greater than 20 minutes and hospital survival: logistic regression (including, if appropriate, random effects of critical care unit/hospital).
- To model time-to-event outcomes: standard survival regression methods such as Weibull and Cox regression.
- To handle interval-censored data: Cox proportional hazards models,^[28] complementary loglog models using partial likelihood estimation (to permit interval censoring) and discretetime hazard models.^[29]
- To account for both interval censoring of the time-to-onset and competition with death: cause-specific Cox proportional hazards models [30] and illness-death models will be considered. [31]
- To model critical care/hospital resource use and costs: multilevel regression models and loglinear regression models.

5.2. Model specification

5.2.1. Risk models for adult general critical care (objective 1)

5.2.1.1. Mortality at 30-days, 90-days and 1-year and time to death (objective 1a)

Outcome defined as death (from any cause) within 30-days, 90-days or 1-year of admission to the critical care unit and number of days from admission to death, established by data linkage with death registrations from ONS.

Patients included in the models will be all those admitted to a critical care unit and discharged alive from the critical care unit.

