5.2.2.2. Mortality at 30-days, 90-days and 1-year (objective 2b)

Outcome defined as mortality at 30-days, 90-days and 1-year using the date of death obtained by data linkage with ONS.

Patients included in the model will be all those admitted to a participating cardiothoracic critical care unit.

The starting point for each new risk model will be the risk model developed in objective 2a.

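### Objective 1a counts survival from unit admission but includes only patients who leave the unit alive, so the unit stay is immortal time that distorts mainly the 30-day and early time-to-death models

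*Protocol*

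**What the plan says.** Protocol section 5.2.1.1 sets the fixed time-point outcome: "Outcome defined as death (from any cause) within 30-days, 90-days or 1-year of admission to the critical care unit". The time-to-event outcome in the same sentence is the "number of days from admission to death". The population follows directly: "Patients included in the models will be all those admitted to a critical care unit and discharged alive from the critical care unit".

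Section 3.2 gives the objective 1 samples both ways, as admissions and as unit survivors: a "total sample size of over 850,000 admissions (700,000 critical care unit survivors) for exploring trends and fit over time". The final models are to be fitted on a subset of 330,000, of whom 280,000 survived the unit. For external validation the section expects that "an additional 170,000 admissions (150,000 critical care unit survivors) will be available".

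Section 5.1.4 names logistic regression for the fixed time-points and, for time-to-event outcomes, standard survival regression with Weibull and Cox as examples. Neither there, nor in 5.2.1.1, nor in Appendix 2 is there any delayed entry, left truncation, landmark or reset of the time origin.

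**The concern.** Time zero is unit admission, but a patient joins the cohort only through a later event, live discharge from the unit. The interval between the two is event-free by design. Its length differs between patients, and anything that lengthens it uses up part of the 30-day, 90-day or 1-year window in which a death could be counted.

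A predictor that prolongs the unit stay, with no bearing on the risk of death afterwards, will therefore be credited with lower mortality. In a Weibull or Cox model run from admission without adjustment, the guaranteed survival time is counted as time at risk. The resulting probability (death by day 30 from admission, given that the patient was later discharged alive) can be defined and a model can be calibrated to it. It is an awkward target, though: the condition is unknown at admission, and the window left after discharge varies from patient to patient. Under objective 4a the models are meant to feed comparative audit reporting, so what they measure should be clear.

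**Working it through.** **Counts in the plan.** In-unit deaths are admissions minus unit survivors, from the rounded figures in section 3.2. The first and third rows match the synopsis.

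| Set | Admissions | Unit survivors | Difference | Share |
|---|---|---|---|---|
| All linked years | 850,000 | 700,000 | 150,000 | 17.6% |
| Model fitting | 330,000 | 280,000 | 50,000 | 15.2% |
| External validation | 170,000 | 150,000 | 20,000 | 11.8% |

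These show the size of the survivor restriction. They do not measure the bias, which comes from the time origin.

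**The mechanism alone.** Assume everyone has the same constant hazard after discharge, h = 0.05/30 per day. For a patient discharged alive after a unit stay of L days,

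P(death within T days of admission) = 1 − exp(−h × max(0, T − L)).

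Counted from discharge, the 30-day risk is 1 − exp(−0.05) = 4.9% for every patient. Counted from admission:

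| Stay L (days) | 30-day risk | 90-day risk |
|---|---|---|
| 1 | 4.7% | 13.8% |
| 7 | 3.8% | 12.9% |
| 14 | 2.6% | 11.9% |
| 21 | 1.5% | 10.9% |
| 30 | 0 | 9.5% |

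Risk after discharge is identical throughout, so the whole gradient comes from the definition.

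**Effect on a predictor.** None of these inputs is in the documents:
- unit stay lognormal, median 2 days, log standard deviation 0.9;
- time from discharge to death Weibull with shape 0.45 and 18% dead at 1 year, so cumulative hazard λt^0.45 with λ = −ln(0.82)/365^0.45 = 0.01395;
- a binary predictor with no effect on post-discharge death that multiplies the stay by m.

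The risk by day T from admission is the mean over L of 1 − exp(−λ × max(0, T − L)^0.45). It was integrated numerically, without sampling error. At 30 days it is 5.95% without the predictor, 5.60% with m = 2 and 4.84% with m = 4. Odds ratios, from unrounded risks, against a true value of 1.0:

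| m | 30 days | 90 days | 1 year |
|---|---|---|---|
| 1.5 | 0.97 | 0.99 | 0.998 |
| 2 | 0.94 | 0.98 | 0.996 |
| 4 | 0.81 | 0.94 | 0.987 |

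**Time to death.** A Cox model on 2 million simulated patients under the same assumptions, clock at admission, gave hazard ratios of about 0.94 (m = 2) and 0.81 (m = 4) with follow-up cut at 30 days, and about 0.995 and 0.98 with follow-up to 1 year. With the clock at discharge, all four were 1.00 to within 0.005. Standard errors of the log hazard ratio were about 0.006 (30 days) and 0.003 (1 year).

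**Comparison within the protocol.** Objective 1c (5.2.1.3) pairs hospital survivors with a window from hospital discharge. Objective 2b (5.2.2.2) includes every unit admission: "Patients included in the model will be all those admitted to a participating cardiothoracic critical care unit". Objective 3b (5.2.3.2) takes all eligible arrests and counts days to death from the arrest. Objective 1a pairs a survivor cohort with a clock that starts before survival was established.

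**The case against.** **The survivor cohort is deliberate.** This stands. Samples are quoted in unit survivors, and section 1.1 gives the aim as mortality beyond the hospital-discharge outcome already modelled. A reader might take the 15% to 18% of admissions left out as the size of the error. It is not: it describes a legitimate choice of population.

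**Audit reporting is not emptied of in-unit deaths.** A reader might infer that a unit's own deaths would vanish from its risk-adjusted results. Section 1.1 says that the improved model for mortality at acute hospital discharge is going into routine reporting, and nothing says that 1a replaces it. In-unit deaths are absent only from the 1a measure. Any incentive tied to when a dying patient is discharged comes with every survivor cohort and would remain with a discharge clock.

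**Populations may differ between objectives.** They do: 1b, 1c and 2c also use survivors, and 2b and 3b inherit their cohorts from 2a and 3a. Differing from 2b and 3b is therefore no fault in itself. The telling comparator is 1c.

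**Details come later.** Section 5.1.4 says that analysis plans will be finalised before modelling, and its survival methods are only examples. Delayed entry could be added then. This answers part of the time-to-death point, but not the fixed time-points, whose origin and cohort are already explicit.

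**The effect is modest outside an extreme case.** This is fair. Only the fourfold stay gives a large distortion, and only at 30 days.

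**Conclusion.** The mismatch is real and follows from two adjacent sentences in section 5.2.1.1. Its direction is structural: whatever lengthens the unit stay looks protective. Its size depends on assumed stay and mortality distributions. For a predictor that doubles to quadruples the stay, the odds ratio is biased to about 0.94 to 0.81 at 30 days and 0.98 to 0.94 at 90 days; at 1 year the bias is only about 0.4% to 1.3%. The time-to-death model is affected mainly in its early part.

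The documents do not support reading this as a fault in the survivor restriction, as a loss of in-unit deaths from existing audit reporting, or as a serious bias at 1 year. The point should be settled before fitting, because it changes the definition of the 1a outcomes.

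**What to change.** Align clock and cohort in section 5.2.1.1, in one of two ways.

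1. Keep the unit survivors (280,000 for fitting) and define the outcomes as death within 30, 90 and 365 days of unit discharge, and time from unit discharge to death. This follows the pattern of objective 1c and respects the evident intention.
2. If mortality from unit admission is the intended target, keep the admission clock and include all unit admissions (330,000 for fitting), as objective 2b does.

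For the time-to-event model only, delayed entry at unit discharge on the admission time scale also removes the immortal time. It is not equivalent to option 1, because it compares patients at equal time since admission. Where risk is highest just after discharge, a longer stay then looks harmful: in the simulation above, the hazard ratio to 30 days was about 1.22 (m = 2) and 1.52 (m = 4). If that route is taken, the plan should say so and allow for time since discharge. Resetting the clock is simpler.

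Unit admission date, unit discharge date and status at unit discharge are already among the Case Mix Programme fields in Appendix 1. No new data are needed, and the cost is a wording change and minor analysis work.
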